### 3 General analysis considerations

### 3.1 Analysis populations

**Primary analysis population**: The primary analysis population will consist of all patients who are randomized and consented to the KP NOURISH study and who survive until hospital discharge, divided into those assigned to MTMs (in addition to Usual Care) and those assigned to receive Usual Care alone. Participants will be analyzed as randomized according to the intention-to-treat principle, regardless of receipt of MTMs.

**Heart failure subpopulation:** The heart failure subpopulation will include all patients in the primary analysis population with pre-existing heart failure as their qualifying medical condition. This population will be analyzed as randomized (MTMs vs. Usual Care) according to the intention-to-treat principle.

**Diabetes subpopulation:** The diabetes subpopulation will include all patients in the primary analysis population with pre-existing diabetes mellitus as their qualifying medical condition. This population will be analyzed as randomized (MTMs vs. Usual Care) according to the intention-to-treat principle.

**Patient reported outcomes subpopulation:** The patient reported outcomes (PRO) subpopulation will include all participants in the primary analysis population with complete baseline and follow-up surveys and excludes participants who died or did not complete the follow-up survey. This population will be analyzed as randomized (MTMs vs. Usual Care) according to the intention to treat principle.

**MTMs subpopulation:** The MTMs subpopulation will include all patients in the primary analysis population who are randomized to either MTMs alone or MTMs with remotely delivered nutritional counseling. This population will be analyzed as randomized (MTMs alone vs MTMs with remotely delivered nutritional counseling) according to the intention-to-treat principle.

**Heart failure MTMs subpopulation:** The heart failure MTMs subpopulation will include all patients with pre-existing heart failure as their qualifying medical condition who are randomized to either MTMs alone or MTMs with remotely delivered nutritional counseling. This population will be analyzed as randomized (MTMs alone vs MTMs with remotely delivered nutritional counseling) according to the intention-to-treat principle.

**Diabetes MTMs subpopulation:** The diabetes MTMs subpopulation will include all patients with pre-existing diabetes as their qualifying medical condition who are randomized to either MTMs alone or MTMs with remotely delivered nutritional counseling. This population will be analyzed as randomized (MTMs alone vs MTMs with remotely delivered nutritional counseling) according to the intention-to-treat principle.

**PRO MTMs subpopulation:** The PRO MTMs subpopulation will include all participants who are randomized to either MTMs alone or MTMs with remotely delivered nutritional counseling that have complete baseline and follow-up surveys. This population will be analyzed as randomized

(MTMs alone vs MTMs with remotely delivered nutritional counseling) according to the intention to treat principle.

#### 3.2 Follow-up and censoring

Participants will be followed for 90 days after discharge for all utilization outcomes and death and will be censored the end of 90 days, loss of KPNC membership or last known contact if they are lost to follow-up.

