10.3 Secondary Clinical Outcomes

Secondary outcomes will include the following:

- 1.) 90-day emergency department visit for any cause
- 2.) 90-day death for any cause
- 3.) Composite of 90-day readmission, emergency department visit, or death for any cause
- 4.) 90-day readmission for heart failure
- 5.) 90-day readmission for diabetes-related complication
- 6.) 60-day readmission for any cause
- 7.) 30-day readmission for any cause

KP NOURISH Study Protocol Version 1.0

All utilization outcomes will be assessed passively using the KPNC EHR which comprehensively captures network and out-of-network hospitalizations or emergency department visits. Hospitalizations for heart failure and diabetes-related complications will be assessed using principal discharge ICD-10 diagnosis codes. Deaths will be assessed through a combination of EHR data and external state death certificate data and Social Security Administration vital status file information. In addition, participants' medical records will be manually reviewed by KPNC DOR research staff for participants whose vital status could not be confirmed through follow-up interviews or participant proxy reporting.

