### 3.4 Missing data

The state-of-the-art EHR at KPNC will be used to identify all hospitalizations and emergency department visits, including any that occur at non-network hospitals given that KPNC is fiscally liable for these types of urgent or emergent resource utilization. Deaths are systematically captured through EHR data (including participant proxy reporting) complemented by external state death certificate data and Social Security Administration vital status file information, with >97% estimated capture based on prior studies involving KPNC members. In addition, all participants' medical records will be manually reviewed for the occurrence of death at the end of follow-up if the research team is unable to reach the participant or their listed secondary contact(s). Thus, it is unlikely to be missing data on clinical outcomes or that data availability will be differentially available between those assigned to MTMs or Usual Care. Participants with missing data from follow-up surveys will be excluded from analyses of patient-reported outcomes.

Missing data on covariates will be described in the baseline table and imputed for use in models, as needed. If less than 5% of covariate data are missing across all covariates of interest, then missing data will be imputed using the median value of each covariate in the full sample. If more than 5% of data are collectively missing for covariates of interest, then a multiple imputation approach will be used to impute data across all covariates.

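### The SAP censors death at plan exit or last contact, although some of its own death sources look beyond both; the 90-day death analysis needs its own follow-up rule

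*SAP*

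**What the plan says.** SAP 3.2 is a single sentence. It begins "Participants will be followed for 90 days after discharge for all utilization outcomes and death and will be censored the end of 90 days, loss", and so takes utilization and death together. Its end points for follow-up apply to both: "death and will be censored the end of 90 days, loss of KPNC membership or last known contact if they are lost to follow-up". No other section of the SAP or protocol gives death a rule of its own.

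Death ascertainment is described in two places. Protocol 10.3 states: "Deaths will be assessed through a combination of EHR data and external state death certificate data and Social Security Administration vital status file information". SAP 3.4 starts from EHR data and proxy reports, "complemented by external state death certificate data and Social Security Administration vital status file information, with >97% estimated capture", a figure that is "based on prior studies involving KPNC members". For participants who cannot be reached, directly or through their listed contacts, SAP 3.4 adds that "medical records will be manually reviewed for the occurrence of death at the end of follow-up".

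For hospitalizations and ED visits, SAP 3.4 gives a different reason for complete capture: the plan is financially liable for urgent care outside its network. Protocol 9.3 expects outcome data for participants who are still active members. It does not address vital status after a participant leaves the plan.

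Death within 90 days is secondary outcome 2. Under SAP 4.2 it is analysed like the primary outcome, with binomial risks, a risk difference and an adjusted Cox hazard ratio, but without a subdistribution hazard ratio.

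**The concern.** Ending follow-up at loss of membership is sound for readmissions and ED visits. Once financial liability ends, the plan may no longer see them. That reason does not carry over to death, because a state death certificate or a Social Security record does not depend on health plan membership.

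The clause on last known contact sits even less well with SAP 3.4. The plan searches the records for deaths among people it cannot reach, yet the censoring rule ends those people's follow-up at the last contact, before any such death.

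At stake is the time-to-event analysis of one secondary outcome, together with its repeat in the two meal arms under SAP 4.4. Plan exit or loss of contact soon after a hospital stay might accompany decline. If so, censoring there would be informative. The documents neither show this nor rule it out.

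**Working it through.** The plan states no figure for death, disenrollment or loss of contact, so there is nothing to reproduce. The check has two parts.

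**1. The rule against the sources**

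| Event type | How it is seen | Does that depend on membership? | Censored at plan exit? |
|---|---|---|---|
| Readmission, ED visit | EHR, plus out-of-network care the plan pays for | Yes | Yes |
| Death, EHR and proxy reports | Plan records and contacts | Probably in part | Yes |
| Death, state and Social Security files | External records | No | Yes |

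Take a participant who leaves the plan on day 40 and dies on day 60, with the death found in the state file. Under SAP 3.2 the Cox model for 90-day death treats this person as censored alive at day 40. The same happens to someone last contacted on day 40 whose death on day 60 is found by record review.

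**2. Size, for plan exit**

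Inputs:
- Sample size 2000 (SAP 2).
- Proportion leaving the plan within 90 days: not given; assumed 1% to 3%.
- 90-day mortality: not given; assumed 3% to 6%, which is 2000 × 0.03 = 60 to 2000 × 0.06 = 120 deaths.
- Exits spread evenly, so on average half the window remains: factor 0.5.
- Risk of death in leavers relative to the average: assumed 1 or 3.

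Deaths set aside = 2000 × leaver proportion × 0.5 × mortality × relative risk.

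- 1% leavers, 3% mortality: 2000 × 0.01 × 0.5 × 0.03 = 0.3; at threefold risk 0.9.
- 3% leavers, 6% mortality: 2000 × 0.03 × 0.5 × 0.06 = 1.8; at threefold risk 5.4.

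As a share of all deaths, mortality cancels. The share is leaver proportion × 0.5 × relative risk: 0.5% to 1.5% at average risk, and 1.5% to 4.5% at threefold risk.

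Wider assumptions (0.5% to 5% leavers, 2% to 6% mortality) give 0.1 to 3.0 deaths at average risk and 0.3 to 9.0 at threefold risk, out of 40 to 120.

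These are upper figures for what the external files could return, since they assume that every such death is found. They do not include deaths after last contact in people who remain members. The documents give no rate for that group.

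**The case against.** The strongest reply is that SAP 3.2 ends follow-up where ascertainment is no longer assured. Protocol 9.3 expects outcome data only for active members, and the >97% capture figure comes from members. A participant who moves out of state may be missed by a state death file. Following leavers to day 90 would then count some of them as alive when their status is unknown. This stands as a real trade-off, and the fix has to acknowledge it. It does not justify setting aside a death that the named sources have recorded within the window.

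Several stronger readings are tempting, and the documents do not support them.

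- A reader might infer that these deaths are already in the data at no further effort. The documents name the external files but do not say that they are searched for people who have left the plan.
- A reader might infer that the Fine-Gray models are distorted, since death is their competing event. Follow-up for readmission and ED visits still properly ends at plan exit, so a later death does not enter those models under either rule. SAP 4.2 computes no subdistribution hazard ratio for death or the composite.
- A reader might infer that the deaths vanish from every analysis. SAP 4.1 does not say how censored participants enter the binomial risks and risk differences, so the loss is clear only for the Cox model.
- A reader might infer bias between the arms. Nothing in the documents suggests that plan exit differs by arm. Protocol 7.5 also excludes planned hospice or facility discharge and life-limiting illness, which makes exit through decline less typical of this cohort.

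**Conclusion.** The point holds as a mismatch between the censoring rule in SAP 3.2 and the death ascertainment in SAP 3.4 and Protocol 10.3. It is confined to the time-to-event analysis of 90-day death. The primary analysis is unchanged.

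The expected effect of plan exit is about zero to two deaths at average risk, and about five at the upper end if leavers have three times that risk. Both figures rest on assumed leaver and mortality rates, exits spread evenly over the window, and full capture after exit. The contribution of the last-contact clause cannot be sized from the documents. This is a worthwhile refinement of low priority, and it would not be expected to change the trial's conclusions.

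**What to change.** In SAP 3.2, give the death endpoint its own rule: follow every participant to day 90 through the EHR and the external death files, without censoring at loss of membership or last known contact. Except participants who revoke authorization, since Protocol 11.4.1 preserves only information collected before revocation. Keep membership censoring for readmission, ED visit and the composite, whose non-fatal parts may not be seen after exit.

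Add three short statements:
- Death capture after plan exit may be less complete than the figure quoted for members.
- A sensitivity analysis of 90-day death will censor at plan exit.
- How censored participants enter the binomial risks and risk differences in SAP 4.1.

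The cost is a few sentences, a separate end date for the death analysis and one extra model. No new type of data source is needed. The sponsor should confirm that the external files are searched for participants who have left the plan; if they are not, those participants need to be added to the search.

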8.1 Follow-up in Usual Care Participants

Following discharge from the index hospitalization, participants randomized to the usual care arm are followed passively by KPNC DOR research staff through the KPNC EHR over the course of the next 10 weeks.

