8.2 Intervention Follow-up

[figure not shown]
8.2.1 10-Week MTMs Delivery

After participants assigned to the MTMs alone or MTMs plus remotely delivered nutritional counseling arms are discharged, KPNC DOR research staff will create Excel files of the discharged participants' intake information and send it to Ceres and POH staff. Ceres and POH staff will contact patients and complete intake within 24 hours of patient discharge from the hospital.

During this initial phone call, Ceres and POH staff will use a structured approach to discuss:

- The participant's health needs
- The participant's current diet
- The MTMs program

Ceres and POH will also schedule the first MTMs delivery date and the weekly delivery times. Ceres and POH will target to deliver the first MTMs within 72 hours and no later than within 1 week of hospital discharge.

Over the course of the next 10 weeks, Ceres and POH delivery drivers will conduct wellness checks to briefly assess the well-being of the participant when they deliver weekly meals. Participants will also complete meal evaluations forms for the past week's meals.

Ceres and POH will document when they are unable to complete a delivery and communicate missed deliveries to the KPNC DOR research team to try to facilitate a successful delivery attempt.

Once the last MTMs delivery is made at the end of 10 weeks, Ceres and POH will inform the KPNC DOR research team and the date of the last meal delivered will be entered into the Appian-based study online tracking system.

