9.3 Loss to Follow-up

For participant's whose status is unclear because they fail to complete study contacts without stating an intention to withdraw, the KPNC DOR research team will show due diligence by attempting to contact the participant, the participant's family and/or listed secondary contact(s), or KPNC primary treating physician. The KPNC DOR research team will also continue to monitor the participant's KPNC EHR data as agreed in the informed consent and will also document in the Appian-based study online tracking system all of the steps taken to contact the participant (i.e. dates of telephone calls, etc.). A participant should not be formally considered lost to follow-up until his/her scheduled end of study visit would have occurred. Outcome data for endpoint ascertainment should be available for all participants with active KPNC membership status.

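### SAP 3.2 censors participants lost to follow-up at last known contact, which discards EHR outcome data that Protocol 9.3 says remain available, and probably discards more in usual care

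*SAP*

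**What the plan says.** SAP 3.2 gives one rule for all utilization outcomes and death: participants "will be censored the end of 90 days, loss of KPNC membership or last known contact if they are lost to follow-up". It does not define contact.

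Protocol 9.3 describes the people concerned as those who "fail to complete study contacts without stating an intention to withdraw". For them, staff will "continue to monitor the participant's KPNC EHR data as agreed in the informed consent". It adds: "Outcome data for endpoint ascertainment should be available for all participants with active KPNC membership status". On timing it says: "A participant should not be formally considered lost to follow-up until his/her scheduled end of study visit would have occurred".

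SAP 3.4 relies on EHR capture in and out of network and concludes: "Thus, it is unlikely to be missing data on clinical outcomes". It also considers differential availability between arms unlikely.

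The contact schedules differ by arm. Usual-care participants are "followed passively by KPNC DOR research staff through the KPNC EHR over the course of the next 10 weeks" (Protocol 8.1), and Protocol section 6 asks them only for a phone survey at 10 weeks. In the meal arms there is an intake call, and then "delivery drivers will conduct wellness checks to briefly assess the well-being of the participant when they deliver weekly meals" (Protocol 8.2.1). The counseling arm adds up to three dietitian visits.

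**The concern.** The primary outcome is read passively from the EHR, so an active member who stops answering calls is still observed. Censoring that person at the last contact removes observed time and observed events from the primary Cox model and, through SAP 4.2, from the secondary clinical outcomes. Because loss is declared only after the end-of-study date, the censoring is applied backwards over follow-up already in hand. That sits badly with the intention-to-treat population in SAP 3.1.

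If contact means study contact, the amount removed depends on assigned arm. Two things are at stake: loss of events, and bias in the primary hazard ratio if people who cannot be reached differ in readmission risk from those who can.

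**Working it through.** **1. Who the clause affects.** SAP 3.2 lists three reasons to censor: day 90, loss of membership, and last contact if lost. People who leave the plan are covered by the second. The third therefore acts mainly on active members, for whom Protocol 9.3 expects outcomes to be available.

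**2. Time discarded per lost person (study-contact reading).** A usual-care participant who misses the week-10 survey was last contacted at the in-hospital baseline call, so all 90 days go. A meal-arm participant with deliveries to about day 63 loses 90 − 63 = 27 days.

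**3. Inputs.** From SAP section 2: 1000 per arm, 10% readmission at 90 days, design hazard ratio 0.68. The documents give no loss rate and no relation between loss and risk, so both are assumed and varied. Hazards are taken as constant.

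**4. Events discarded when loss is unrelated to risk.** Take 10% as the usual-care rate and the hazard ratio as 0.68. The daily hazard is −ln(0.9)/90 = 0.001171 in usual care and 0.68 times that in the meal arms. Meal-arm risk is 6.91% by day 90 and 4.89% by day 63.
- 10% lost, usual care: 1000 × 0.10 × 0.10 = 10.0 events.
- 10% lost, meal arms: 1000 × 0.10 × (0.0691 − 0.0489) = 2.0 events, or 4.2 if the last contact is day 35.
- 5% lost: 5.0 versus 1.0. 20% lost: 20.0 versus 4.0.

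The hazard ratio is unbiased here; the cost is precision. The plan gives no figure for this loss, only 80% power overall. With Schoenfeld's formula, power = Φ(√(E/4) × |ln 0.68| − 1.96), that figure comes out at 77.9% if 10% is the overall rate (E = 200) and 70.8% if it is the usual-care rate (E = 169). The SAP does not say which is meant, and that is a separate matter. On the usual-care reading, 10% loss leaves E = 90.0 + 67.1 = 157.1 and power 67.6%, a fall of about 3 points.

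**5. Bias when loss is related to risk, with no true effect.** Let a fraction f be lost in each arm, with k times the hazard of the rest. Reachable patients have hazard λ = [−ln(0.9)/90]/(1 − f + fk). Lost usual-care patients contribute no time. Lost meal-arm patients contribute to day 70, or to a day spread evenly over days 7 to 70. The apparent hazard ratio is the ratio of events per person-day.

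Worked case, f = 0.15, k = 2: λ = 0.001171/1.15 = 0.001018.
- Usual care, per 1000: 850 × (1 − e^(−90λ)) = 74.4 events, against about 100 with full follow-up; mean time 73.1 days.
- Meal arms, day 70: 74.4 + 150 × (1 − e^(−140λ)) = 94.3 events; mean time 82.9 days.
- Ratio: (94.3/82.9)/(74.4/73.1) = 1.12. With spread censoring: (85.6/78.6)/(74.4/73.1) = 1.07.

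| Lost per arm | Hazard of lost | HR, day 70 | HR, spread |
|---|---|---|---|
| 5% | double | 1.04 | 1.02 |
| 10% | double | 1.08 | 1.05 |
| 15% | double | 1.12 | 1.07 |
| 20% | double | 1.16 | 1.10 |
| 15% | same | 1.00 | 1.00 |
| 15% | half | 0.94 | 0.96 |

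Solving the Cox score equation instead gives nearly the same values.

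**The case against.** The best defense is that few people may ever be classed as lost. Protocol 9.3 withholds that status until the end-of-study visit would have passed and first requires attempts through family, secondary contacts or the treating physician. The note to the Schedule of Assessments allows a visit to be a data pull. SAP 3.4 deals with survey non-response separately, and no passage equates a missed week-10 survey with loss for clinical outcomes. This stands as a limit on the size. It does not rescue the clause: if it catches nobody it is unnecessary, and if it catches active members it contradicts Protocol 9.3.

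The contrast between arms is also less clean than the schedule suggests. Meal-arm participants who cannot receive meals are followed passively, deliveries can be paused for up to two consecutive weeks, and participants may stop meals. That narrows the gap. If contact meant an EHR encounter, the same rule would apply to both arms, but lost patients with no event and no encounter would leave at discharge while those with events were counted. Leaving the term undefined is part of the problem.

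Adjustment for severity, predicted readmission risk and multimorbidity would reduce the bias to the extent that being unreachable tracks those measures.

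Three further inferences are tempting but not supported:
- **That the dead stay at risk to day 90 in the Cox model because SAP 3.2 omits death.** SAP 4.1 specifies a separate Fine-Gray model for the competing risk of death, which implies that the Cox model censors at death. This is an omission of wording.
- **That usual care has only 10 weeks of outcome follow-up.** Protocol section 6, Protocol 10.2 and SAP 3.2 all give 90 days.
- **That the crude risks and Wald risk differences are wrong in themselves.** As far as this clause goes, they are distorted only if its censoring is carried into the counts. With no true effect, 10% loss unrelated to risk and meal-arm censoring at day 63, the shift would be 9.71% − 9.00% = 0.71 points against the meals.

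**Conclusion.** The point holds as an inconsistency in the rule governing the primary analysis. SAP 3.2 discards outcome follow-up that Protocol 9.3 and SAP 3.4 say is available and, on the study-contact reading, discards more of it in usual care.

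A reader might infer that the primary hazard ratio is bound to be biased against the meals. The documents do not support that. With loss unrelated to risk there is no bias in the hazard ratio, only fewer events. With loss related to risk the sign follows the relation: roughly 1.02 to 1.04 at 5% loss and 1.07 to 1.12 at 15% if lost patients have double hazard, and 0.94 to 0.96 at 15% if they have half. These figures rest on assumed loss rates and hazards, constant hazards, no covariate adjustment and equal loss in both arms. The true size cannot be known from the plan.

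**What to change.** In SAP 3.2, for EHR-captured utilization outcomes and death:
- Delete the last-contact clause. Censor only at day 90, loss of KPNC membership or revoked authorization.
- Name death as a censoring event in the cause-specific Cox models for non-fatal outcomes and as the competing event in the Fine-Gray models, as SAP 4.1 implies.
- Ascertain death to day 90 through the EHR and vital-status files.
- Confine missed study contacts to the survey outcomes.

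As a minor wording point, reconcile the 10 weeks of EHR follow-up in Protocol 8.1 with the 90 days stated elsewhere.

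The cost is a few lines in the SAP and one in the protocol. The data are already planned for collection, and under the revised rule no event observed in an active member with authorization in force is discarded, whatever the rate of missed contacts.
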